5.0 Methods

5.1 Measures

The following outcome, safety, and process measures will be used in the study. This study will utilize methods described in the Treatment Manual for conducting MDMA-assisted Psychotherapy combined with methods from the CBCT for PTSD manual. The integration of these manuals will provide the researcher with a consistent psychotherapy approach and test an investigational form of drug-assisted psychotherapy. The Treatment Manual is not intended to define all interactions that occur in the therapy. All psychotherapy sessions, including Experimental Sessions, may be recorded to audio and video, with all recordings preserved for research and training purposes.

Page 32 of 89

Table 4: Study Measures

Measure	Purpose	Administration	Time/ # of items	When	PTSD+ Participant	CSO Participant
Screening, Inclusion & Exclusion						
SCID for DSM-5- AXIS 1 only and then screening question for AXIS 2 modules (do modules if needed)	Screening	Interview	60 minutes	Baseline	Y	Y
Primary & Secondary Outcomes						
CAPS-5 Clinician Administered PTSD Scale for DSM-5	PTSD Severity	Interview	90 minutes	Baseline, Endpoint, LTFU 3, 6	Y	N
PCL (last month) PTSD Checklist for DSM-5	PTSD symptoms	Self-report	10-15 minutes	Baseline (with LEC), Endpoint, LTFU 3, 6	Y	Y (PCL- Participant)
PCL (since last visit) PTSD Checklist for DSM-5	PTSD symptoms	Self-report	10-15 minutes	Integrative Sessions, Midpoint	Y	Y (PCL- Participant)
PCL (since last week) PTSD Checklist for DSM-5	PTSD symptoms	Self-report	10-15 minutes	Visit 2	Y	Y (PCL- Participant)
BDI-II Beck Depression Inventory	Depression Symptoms	Self-report	5-10 minutes	Baseline, Midpoint, Endpoint, LTFU 3, 6	Y	Y
ERQ Emotional Regulation Questionnaire	Emotion regulation	Self-report	4-6 minutes	Baseline, Midpoint, Endpoint, LTFU 3, 6	Y	Y
IRI Interpersonal Reactivity Index	Compassion empathy, social functioning	Self-report	10 minutes	Baseline, Day after Experimental Sessions, Midpoint, Endpoint, LTFU 3, 6	Y	Y
PSQI Pittsburg Sleep Quality Index	Sleep Quality	Self-report	5-10 minutes	Baseline, Midpoint, Endpoint, LTFU 3, 6	Y	Y
PTGI Post Traumatic Growth Inventory	Growth after Trauma	Self-report	5-10 minutes	Baseline, Midpoint, Endpoint, LTFU 3, 6	Y	Modified for participant. Participant will rate the PTSD participant. Y
TAS-20 Toronto Alexithymia Scale	Emotion recognition, alexithymia	Self-report	5 minutes	Baseline, Midpoint, Endpoint, LTFU 3, 6	Y	Y

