The secondary measure of PTSD symptoms will be the PCL (reported for last month, since last visit, and since last week per Table 4), a self-report measure designed to follow DSM-5 criteria for assessing PTSD. The PTSD Checklist (PCL-5) [137] is a 20-item selfreport questionnaire in which respondents indicate the presence and severity of PTSD symptoms, derived from the DSM-5 symptoms of PTSD [36]. Participants indicate how much distress they have experienced due to symptoms such as "Repeated, disturbing memories, thoughts, or images of a stressful experience from the past," "Trouble remembering important parts of a stressful experience from the past," and "Feeling irritable or having angry outbursts" on a five-point Likert-type scale (1 = not at all, 5 = extremely). The total PCL-5 score (a sum of all 20 items) provides an index of overall PTSD symptom severity. Reports on reliability and validation of the PCL-5 are underway; preliminary comparison with the PCL for DSM IV suggests that the cut-off for PCL-5 is 11 to 14 points lower than for the PCL [137]. Participants will complete the PCL-5 questionnaire, as specified in Table 3: Time and Events. The PTSD+ participant will complete it based on their own symptoms and the CSO participant will complete it based on the PTSD+ participant.

The BDI-II is a 1996 revision of the BDI, a 21-item self-report measure [138, 139] that will serve as a measure of depression according to DSM-IV criteria [140]. The BDI-II has been validated, has high internal consistency and good test/re-test reliability, and is not overly sensitive to daily variations in mood. It takes five to ten minutes to complete [140]. Score cutoffs indicate: 0-13 minimal depression, 14-19 mild depression, 20-28 moderate depression, and 29-63 severe depression. Initial and subsequent studies report that the BDI-II total score has a reliability coefficient of 0.90 to 0.91 and that it is related to other measures of depression symptoms [140, 141]. Higher scores indicate more severe depressive symptoms. Both the participants will complete the BDI-II according to Table 3: Time and Events.

The ERQ is a brief measure of self-reported emotion-regulation. It consists of ten items that is intended to assess means of coping with emotions via changing them, as through reappraisal, or suppressing them [142]. Respondents rate indicate the extent of their

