A blinded IR who will not be present during any of the therapy sessions will administer:

• Structured Clinical Interview for DSM-5 Diagnoses (Research Version) (SCID-RV) to assess eligibility based on Axis I diagnoses, which includes a self-report questionnaire to focus on modules to use based on symptoms for both the PTSD+participant and CSO participant

Page 43 of 89

- SCID-II Axis 2 questionnaire to determine if specific modules of the SCID-II Interview will be conducted to confirm diagnoses of personality disorders
- Last-month CAPS for the PTSD+ participant to assess PTSD symptoms and eligibility, which may be recorded to video in as many instances as necessary to establish inter-rater reliability

The following self-report measures will be completed:

- PTGI (in reference to time since the trauma) for the PTSD+ participant and modified for the CSO participant to rate the PTSD+ participant
- PCL-5 (last month) to assess PTSD symptoms for the PTSD+ participant and modified for the CSO participant to rate the PTSD+ participant.
- TABS to assess trauma related beliefs for the PTSD+ participant and modified for the CSO participant to rate the PTSD+ participant
- MDI to assess dissociative symptomology for the PTSD+ participant and CSO participant
- SORTS to assess partner accommodation for the CSO participant
- BDI-II to assess depression symptoms for both the PTSD+ participant and CSO participant
- PSQI to assess sleep quality for both the PTSD+ participant and CSO participant. PSQI-PTSD Addendum will be assessed for the PTSD+ participant only
- ERQ to assess emotional regulation for both the PTSD+ participant and CSO participant
- TAS-20 to assess emotion recognition, alexithymia for both the PTSD+ participant and CSO participant
- QRI to assess relationship satisfaction for both the PTSD+ participant and CSO participant
- CTS to assess conflict, tactics and aggression for both the PTSD+ participant and CSO participant
- IPF to assess psychosocial functioning for both the PTSD+ participant and CSO participant
- MSIS to assess social intimacy for both the PTSD+ participant and CSO participant
- IRI to assess compassion, empathy and social functioning for both the PTSD+ participant and CSO participant
- IPC for both the PTSD+ participant and CSO participant
- CSI for both the PTSD+ participant and CSO participant, if in a romantic relationship

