5.2.5 Daily Telephone Contact for Seven Days after an Experimental Session

During daily phone contact:

- a. Starting on the day of the Integrative Session following each Experimental Session, one of the therapists will contact the PTSD+ participant and CSO participant via telephone, telemedicine, or in person every day for one week. The goal of daily contact is assessment of changes in General Wellbeing, safety, and offering support.
- b. The telephone contact will be for a brief check-in lasting five to 15 minutes, or as long as necessary to address any participant's concerns and to assess participants' wellbeing. Additional telephone contact can be initiated at the request of the therapists or participant.
- c. On the second and seventh day of contact after the Experimental Session, the therapists will administer the C-SSRS.
- d. General Wellbeing will be assessed at each phone call.
- e. Spontaneously reported reactions, AEs and Medications will be collected, as described in Sections 8.0 and 9.0.

5.2.6 Integrative Sessions Between Experimental Sessions (Visits 5, 6, 7, 8, 12, 13, 14, and 15 - Telemedicine Visits)

Visits 5, 6, 7, and 8 will occur over 3 weeks between Experimental Sessions 1 and 2 (Visits 3 and 10); Visits 12, 13, 14, 15 will occur over 4 weeks following Visit 10.

CBCT Manual Sessions Review, 6, 7, 8, 9, 12, 13, 14, and 15

Sessions 6 (visit 5) and 7 (visit 6)—Getting UNSTUCK (learning the process of dyadic cognitive restructuring) and problem solving.

Sessions 8 (visit 7) and 9 (visit 8) – Making meaning of the trauma, specifically regarding acceptance and blame.

Sessions 12 (visit 12), 13 (visit 13), 14 (visit 14), and 15 (visit 15) – Making meaning of the trauma. Discussion specifically of themes of emotional closeness, physical closeness, posttraumatic growth, and review and reinforcement of treatment gains.

After each Experimental Session, in addition to the session the following morning, the PTSD+ participant and CSO participant will have four additional Integrative Sessions with the therapists lasting 75-90 minutes each. The therapists may conduct more sessions if they and the PTSD+ participant deem it necessary.

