5.2.7 Evaluation and Preparation Visit at Midpoint (Visit 9 - Clinic Visit)

(Approximately 3 weeks after V3; prior to V10)

CBCT Manual Sessions 10 and 11

Sessions 10 and 11 – Making meaning of the trauma. Discussion of the themes of trust and control.

The midpoint evaluation will occur approximately 20 days after the first Experimental Session. Dyads who have withdrawn from treatment but have continued for follow-up will also complete this time point. This session will be recorded to audio/video.

- a. The therapists will assess suicidal ideation and behavior with the C-SSRS
- b. General Wellbeing will be assessed
- c. Collect AEs and medications, as described in Sections 8.0 and 9.0

The following self-report measures will be completed at the midpoint:

- PTGI (in reference to time since the trauma) for the PTSD+ participant and modified for the CSO participant to rate the PTSD+ participant
- PCL (since last visit) to assess PTSD symptoms for the PTSD+ participant and modified for the CSO participant to rate the PTSD+ participant
- TABS to assess trauma related beliefs for the PTSD+ participant and modified for the CSO participant to rate the PTSD+ participant
- MDI to assess dissociative symptomology for the PTSD+ participant and CSO participant
- SORTS to assess partner accommodation for the CSO participant
- BDI-II to assess depression symptoms for both the PTSD+ participant and CSO participant
- PSQI to assess sleep quality for both the PTSD+ participant and CSO participant.
 PSQI PTSD addendum will be completed by PTSD+ participant only
- ERQ to assess emotional regulation for both the PTSD+ participant and CSO participant
- TAS-20 to assess emotion recognition, alexithymia for both the PTSD+ participant and CSO participant
- QRI to assess relationship satisfaction for both the PTSD+ participant and CSO participant
- CTS to assess conflict, tactics and aggression for both the PTSD+ participant and CSO participant
- IPF to assess psychosocial functioning for both the PTSD+ participant and CSO participant
- MSIS to assess social intimacy for both the PTSD+ participant and CSO participant
- IRI to assess compassion, empathy and social functioning for both the PTSD+ participant and CSO participant

- IPC for both the PTSD+ participant and CSO participant
- CSI for both the PTSD+ participant and CSO participant, if in a romantic relationship

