#### **Baseline Values**

Baseline values are from screening/baseline visit for all measures, except CAPS-5 and C-SSRS. Baseline CAPS-5 will be assessed, during screening (pre-study), no more than 8 weeks before the first experimental session. This allows adequate washout of at least five half-lives of pre-study psychiatric medications and active metabolites, plus one week for stabilization. If CAPS-5 is completed outside of this window for a participant, the PI will consult the CRA and Medical Monitor to determine if the Baseline CAPS should be repeated. For C-SSRS, pre-enrollment scores will be used as a measure of 'lifetime' suicidal ideation and behavior, and preparatory session 2 (visit 2) prior to drug administration will used as 'baseline.' If a subject was not administered the C-SSRS at preparatory session 2 (visit 2), then 'baseline' scores will be visit 3 pre-drug C-SSRS observation.

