## 2. Secondary and Exploratory Efficacy Analyses

Efficacy of secondary and other exploratory outcome measures will be assessed at baseline, midpoint (visit 9), and primary endpoint (visit 16) to examine change in scores over time in the total sample, and separately, by PTSD+ participants and CSO participants.

For each model, a one-way repeated-measures ANOVA with post-hoc contrast comparisons will be conducted to test the effects of the treatment on: PTSD CAPS-5; Significant Others' Responses to Trauma Scale (SORTS); Posttraumatic Stress Disorder Checklist for the DSM-5 (PCL-5); Beck Depression Inventory-II (BDI-II); Emotion Regulation Questionnaire (ERQ); Pittsburgh Sleep Quality Index (PSQI); Posttraumatic Growth Inventory (PTGI); Toronto Alexithymia Scale-20 (TAS-20); Inventory of Psychosocial Functioning (IPF); Revised Conflict Tactics Scale (CTS-2); Trauma and Attachment Beliefs Scale (TABS); and Multiscale Dissociation Inventory (MDI). Relationship distress outcome measures include: Interpersonal Reactivity Index (IRI); Quality of Relationships Inventory (QRI); Miller Social Intimacy Scale (MSIS); Interpersonal Closeness Measure (IPC); and Couples Satisfaction Index (CSI).

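### PCL-5 recall changes from last month to since last visit at Visit 9, so the omnibus test and every contrast involving Visit 9 mix recall length with change over treatment

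*Protocol*

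**What the plan says.** Protocol 5.1.1 states that the PCL-5 is "reported for last month, since last visit, and since last week per Table 4". Table 4 and the visit descriptions assign the versions as follows.

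- **Last month:** screening baseline, Visit 16, Visit 17 and Visit 18. Section 5.2.1 lists "PCL-5 (last month) to assess PTSD symptoms for the PTSD+ participant and" the concerned significant other's rating; 5.2.8 and 5.2.9 use the same recall.
- **Last week:** Visit 2 only (5.2.3).
- **Since last visit:** Table 4 gives the timing for "PCL (since last visit) PTSD Checklist for DSM-5" as "Integrative Sessions, Midpoint". Section 5.2.7 confirms it for Visit 9: "PCL (since last visit) to assess PTSD symptoms for the PTSD+ participant and" the concerned significant other.

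Under Baseline Values, the SAP says: "Baseline values are from screening/baseline visit for all measures, except CAPS-5 and C-SSRS". The PCL-5 baseline in the models is therefore the last-month screening score. SAP Efficacy section 2 says that secondary and exploratory measures "will be assessed at baseline, midpoint (visit 9), and primary endpoint (visit 16) to examine change in scores over time", using a one-way repeated-measures ANOVA with post-hoc contrasts as the test of treatment effect; PCL-5 is on the list. Efficacy section 3 adds Visits 17 and 18, keeps Visit 9, and uses ANCOVA, or MMRM if dropout leaves data missing. SAP 5.1 names the three recall versions but does not say which enters which model.

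Protocol 12.0 also plans a linear mixed-effects regression of PCL-5 over 15 time points from the second preparatory visit, with week as a continuous variable.

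**The concern.** A repeated-measures model reads differences between visits as change in the participant. Here the question changes too. At baseline and Visit 16 it covers a month; at Visit 9 it covers the time since Visit 8. Any effect of window length on the score falls exactly where the model looks for an early treatment effect, and it may appear as a second change between Visit 9 and Visit 16.

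Three features of the design make this hard to detect. There is no control arm in which a recall artefact could cancel. CAPS is not given at Visit 9 (Table 3), so PCL-5 is the only dedicated PTSD symptom scale at that visit. And PCL-5 change at the midpoint is a stated objective, with PCL-5 meant to support the CAPS (protocol 3.2 and 12.0). For CAPS itself the protocol fixes last-month recall at every assessment (5.1.1); PCL-5 has no matching safeguard.

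**Working it through.** **1. Which version enters which model**

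| Analysis | Last month | Since last visit | Last week |
|---|---|---|---|
| SAP Efficacy 2 (ANOVA) | baseline, V16 | V9 | none |
| SAP Efficacy 3 (ANCOVA/MMRM) | baseline (covariate), V16, V17, V18 | V9 | none |
| Protocol 12.0 (15-point regression) | V16, V17, V18 | V4–V9, V11–V15 | V2 |

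The protocol's count of 15 reproduces from Table 3: V2 (1) + V4–V8 (5) + V9 (1) + V11–V15 (5) + V16–V18 (3) = 15. By version, that is 1 last-week, 5 + 1 + 5 = 11 since-last-visit, and 3 last-month.

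**2. Length of the Visit 9 window**

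Protocol 5.2.6 says: "Visits 5, 6, 7, and 8 will occur over 3 weeks between Experimental Sessions 1 and 2". Visit 4 is one day after Visit 3, and Visit 9 closes the fifth interval after Visit 4. With even spacing (an assumption), window = (midpoint day after V3 − 1) / 5.

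- Midpoint at 20 days (5.2.7): 19 / 5 = 3.8 days
- Midpoint at 3 weeks (Table 3): 20 / 5 = 4.0 days
- Midpoint at 2 weeks (note under Table 4): 13 / 5 = 2.6 days

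Against about 30 days, the ratios are 30 / 3.8 = 7.9, 30 / 4.0 = 7.5 and 30 / 2.6 = 11.5. The one-day windows at Visits 4 and 11 occur only in the protocol's 15-point regression.

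**3. What an artefact would do with n = 10**

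The method was first checked on the protocol's own power figure. For an exact two-sided paired t-test with n = 10, effect size 0.8 and alpha 0.05, the noncentrality is 0.8 × √10 = 2.53 on 9 df. The power is 0.616, which matches the stated 62%.

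Next, assume no true change at all, but a recall shift at Visit 9 of b SD of the paired difference. The baseline–V9 column is exact (noncentrality b × √10). The other columns are simulated (20,000 runs, three time points, correlation 0.5 assumed).

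| b | Baseline–V9 | Omnibus F | V9–V16 | Baseline–V16 |
|---|---|---|---|---|
| 0.2 | 8.8% | 8.7% | 9.2% | 4.8% |
| 0.5 | 29% | 31% | 29% | 5.1% |
| 0.8 | 62% | 67% | 62% | 5.1% |

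With b = 0, as when all three time points share one recall period, every simulated rate is close to 5% (5.0% to 5.2%). The values of b are assumptions; nothing in the documents points to one of them.

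**The case against.** **The main comparison is sound.** Baseline and Visit 16 both use last-month recall, and the SAP already plans post-hoc contrasts, so the like-for-like comparison is available. This stands. A reader might infer that the whole PCL-5 change analysis, or even the primary result, is confounded. The documents do not support that: CAPS uses last-month recall throughout, and PCL-5 at Visits 17 and 18 also matches baseline.

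**The mechanism is not documented.** A reader might infer that a short window must lower the score and so flatter the midpoint. But 5.1.1 describes PCL-5 as a rating of how much distress symptoms caused, not a count of occurrences. That a shorter window gives symptoms fewer chances to occur is plausible reasoning, but the documents establish neither the direction nor the size. This stands too.

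**A shorter midpoint window has a rationale.** Visit 9 is about 20 days after the first Experimental Session, so a 30-day form would reach back about 10 days before it. That justifies a different form at Visit 9. It does not justify entering that form in the same model as the last-month form.

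**The few-day window is inferred.** No section fixes the gap from Visit 8 to Visit 9. Therapists may add sessions (5.2.6) and delays extend the schedule (4.1). The 2.6 to 4 days is therefore conditional on even spacing. A variable window is still not a one-month window.

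**The stakes are limited.** PCL-5 is secondary in a 10-dyad open-label pilot, and protocol 12.0 exempts it from the 0.05 threshold. The SAP applies 0.05 to all tests without that exemption.

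Two further inferences fail. The one-day windows are not part of either SAP model. And Visit 2 is not unused: it starts the protocol's 15-point regression, although the SAP models omit it.

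**Conclusion.** The point holds within limits. In SAP Efficacy section 2, the PCL-5 omnibus test and both contrasts involving Visit 9 mix recall length with treatment effect. The same applies to comparisons involving Visit 9 in the long-term model. The protocol's 15-point regression has the problem in a wider form, because one slope is fitted through three recall periods. The baseline-to-Visit 16 contrast and the CAPS primary analysis are unaffected.

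The difference in recall is documented. Its length, about 30 days against roughly 2.6 to 4, rests on even visit spacing and on which midpoint timing applies. The bias in PCL-5 points cannot be derived, and the rejection rates above only illustrate how sensitive a 10-participant analysis would be. This should be corrected before the SAP is finalised; it does not threaten the primary conclusion.

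**What to change.** In the SAP:

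1. State which recall version enters each PCL-5 analysis.
2. Restrict the PCL-5 change-from-baseline models to last-month scores: baseline, Visit 16, Visit 17 and Visit 18.
3. Analyse the since-last-visit scores (Visits 4–9 and 11–15) as a separate within-treatment series. Do not fit last-month scores in the same slope, and bring the protocol's 15-point regression into line with this.
4. Optionally, give the last-week form at Visit 9 and use Visit 2 as its matched one-week reference.

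In the protocol, reconcile the midpoint timing in the note under Table 4 (2 weeks) with Table 3 and 5.2.7 (about 3 weeks, or 20 days), because it determines the window length.

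Steps 1 to 3 need wording only, and the SAP says it will be finalised before any analysis, so they can be prespecified. The cost is that the midpoint loses its direct contrast with the screening baseline. Step 4 needs one form change and has two further costs: Visit 9 leaves the since-last-visit series, and Visit 2 is a post-washout reference for participants who tapered medication, whereas their screening score may precede the washout (protocol 4.1 and 5.2.3).

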5.1.1 Outcome Measures

The primary measure will be change in CAPS scores from Baseline to Primary Endpoint. A qualified, blinded IR will perform the CAPS at Baseline and outcome measurement time points. The IR will not be present during the participant's Experimental Sessions nor have any information regarding the Experimental Sessions. CAPS-5 [136] is a semi-structured clinical interview used to assess index history of DSM-5-defined traumatic event exposure [36], including the most distressing event, time since exposure, and total number of exposures, as well as frequency and severity of posttraumatic stress symptoms, as evidenced by CAPS total score. The CAPS provides diagnostic status (presence versus absence) of PTSD as well as PTSD symptom severity. Changes in the CAPS total score will be used as the primary PTSD outcome measure, and will be the primary determinant of effect size for this pilot study. All assessments, including those at Baseline, will use the CAPS assessment of symptoms over the last month. The IR will administer the CAPS at visits described in Table 3: Time and Events either in person or via telemedicine. Studies for validation of this measure are ongoing.

The secondary measure of PTSD symptoms will be the PCL (reported for last month, since last visit, and since last week per Table 4), a self-report measure designed to follow DSM-5 criteria for assessing PTSD. The PTSD Checklist (PCL-5) [137] is a 20-item selfreport questionnaire in which respondents indicate the presence and severity of PTSD symptoms, derived from the DSM-5 symptoms of PTSD [36]. Participants indicate how much distress they have experienced due to symptoms such as "Repeated, disturbing memories, thoughts, or images of a stressful experience from the past," "Trouble remembering important parts of a stressful experience from the past," and "Feeling irritable or having angry outbursts" on a five-point Likert-type scale (1 = not at all, 5 = extremely). The total PCL-5 score (a sum of all 20 items) provides an index of overall PTSD symptom severity. Reports on reliability and validation of the PCL-5 are underway; preliminary comparison with the PCL for DSM IV suggests that the cut-off for PCL-5 is 11 to 14 points lower than for the PCL [137]. Participants will complete the PCL-5 questionnaire, as specified in Table 3: Time and Events. The PTSD+ participant will complete it based on their own symptoms and the CSO participant will complete it based on the PTSD+ participant.

The BDI-II is a 1996 revision of the BDI, a 21-item self-report measure [138, 139] that will serve as a measure of depression according to DSM-IV criteria [140]. The BDI-II has been validated, has high internal consistency and good test/re-test reliability, and is not overly sensitive to daily variations in mood. It takes five to ten minutes to complete [140]. Score cutoffs indicate: 0-13 minimal depression, 14-19 mild depression, 20-28 moderate depression, and 29-63 severe depression. Initial and subsequent studies report that the BDI-II total score has a reliability coefficient of 0.90 to 0.91 and that it is related to other measures of depression symptoms [140, 141]. Higher scores indicate more severe depressive symptoms. Both the participants will complete the BDI-II according to Table 3: Time and Events.

The ERQ is a brief measure of self-reported emotion-regulation. It consists of ten items that is intended to assess means of coping with emotions via changing them, as through reappraisal, or suppressing them [142]. Respondents rate indicate the extent of their

agreement or disagreement with each item by selecting a point on a 7-point Likert scale, where 1= strongly disagree and 7 = strongly agree. The ERQ should take four to six minutes to complete. Specific items are summed to produce two separate scales, Reappraisal and Suppression. The measure is reliable, with Reappraisal obtaining a Cronbach's alpha of 0.79 and Suppression an alpha of 0.73, and test-retest reliability of 0.69 [142], and scores on the ERQ are correlated with other measures of degree of emotional expressivity. The ERQ will be completed by both the PTSD+ participant and the CSO the participant according to Table 3: Time and Events.

The IRI assesses four aspects of empathy: social functioning, self-esteem, emotionality, and sensitivity to others [143-145]. Empathy is not a discrete emotion. More accurately, empathy is a set of constructs. Therefore, the IRI accounts for the fact that each construct concerns an individual's responses to the observed experiences of other people, yet each construct is distinctive from the others. The self-report questionnaire includes 28 items that are rated on a 5-point, Likert-type scale. The four 7-item subscales include two measures of cognitive empathy and two measures of affective empathy. The internal reliabilities for the four scales range from 0.71 to 0.77, and test-retest reliabilities range from 0.62 to 0.71 [143, 144]. The IRI will be completed by both the PTSD+ participant and the CSO participant, according to Table 3: Time and Events.

The PSQI is a measure of self-reported sleep quality over a one-month period. The PSQI was designed to be a reliable, standardized measure able to distinguish between good and poor sleepers. It consists of 19 items, with possible responses ranging from 0 to 4 on a five-point scale [146]. The PSQI consists of seven sub-scales; sleep quality, sleep latency, sleep duration, habitual sleep efficiency, sleep disturbance, use of sleeping medications, and daytime dysfunction. These are all summed to produce a single global scale. Global scores can range from 0 to 21, with higher scores reflecting poorer sleep quality, and a score below five indicative of good sleep. It takes five to 10 minutes to complete. Test-retest reliability ranges from 0.85 to 0.87, and it is internally consistent, with a Cronbach's alpha of 0.83 [146, 147]. Global scores correlate with other measures of alertness and self-reported sleep quality [143]. The Pittsburgh Sleep Quality-PTSD Addendum [148] is a seven-item addendum for the PSQI that assesses disruptive nocturnal behavior specific to PTSD (e.g., hot flashes, nervousness, trauma nightmares). The PTSD+ participant will indicate the presence and severity of trauma-related sleep disturbances. Both the PTSD+ participant and the CSO participant will complete the PSQI according to Table 3: Time and Events.

The PTGI is a 21-item self-report measure of perceived growth or benefits occurring after a traumatic event. It contains five subscales: relationship to others, new possibilities, personal strength, spiritual change, and appreciation of life [149, 150]. In this study, participants will complete the PTGI in reference to the time since the trauma at Baseline, but will respond in reference to the beginning of their participation in the study on all subsequent occasions. PTGI sub-scale scores are reliable, with reliability coefficients ranging from 0.83 to 0.90, and the scale scores were moderately related to each other [149, 151]. PTGI scores are corroborated by others' assessments of posttraumatic growth, suggesting that the measure has convergent validity [152, 153]. Both the PTSD+ participant and the CSO participant will complete the PTGI according to Table 3: Time and Events.

The TAS-20 is a 20-item measure of self-reported difficulties with recognizing and verbalizing emotions [154, 155]. Responses are made on a 5-point Likert scale where 1 = strongly disagree and 5 = strongly agree. Estimated time of measurement is 5 to 10 minutes. The scale is comprised of three subscales; Difficulty Describing Feelings, Difficulty Identifying Feelings and Externally-Oriented Thinking, with all scales summed to create a total score reflecting presence and degree of alexithymia. The TAS-20 can be used diagnostically with a score of 61 or higher indicative of alexithymia. The TAS-20 is reliable and has good test-retest reliability (Cronbach's alpha = 0.81, test-retest of 0.77). It is an established measure of alexithymia. There is some suggestion of an overlap between this condition and Asperger's syndrome, with samples of people with Asperger's syndrome showing greater rates of alexithymia than age and gender-matched controls [156, 157]. The TAS-20 will be completed by both the PTSD+ participant and the CSO participant (modified) according to Table 3: Time and Events.

The Quality of Relationships Inventory (QRI) is used to assess the supportive and conflictual aspects of close relationships [158]. The QRI presents an overview of approaches taken to study the social support construct. The QRI emphasizes the role of situational, intrapersonal, and interpersonal contexts in social support processes. The QRI possesses good to excellent reliability, ranging from 0.7 to 0.9 and moderate to good testretest stability (0.48 to 0.79) [159, 160]. Both the PTSD+ participant and the CSO participant will complete the QRI according to Table 3: Time and Events.

The Significant Others' Responses to Trauma Scale (SORTS) [9] is a 14-item self-report measure of relationship problems and psychological distress faced by partners of people with PTSD. Each behavior or issue listed is rated on a five-point Likert scale (anchored at 0-4) for frequency of the behavior or issue and degree of distress the behavior or issue causes for the partner. The SORTS demonstrates strong internal consistency. It has Cronbach's alpha for the total scale of 0.93 and alphas of 0.86 for frequency and 0.87 for intensity (degree of distress) scores, and associations with individual and relationship distress, including a positive correlation between SORTS score and PTSD symptom severity in the partner with PTSD, and between SORTS score and depressive symptoms in the partner without PTSD. The PTSD+ participant and the CSO participant will complete the SORTS about the PTSD+ participant according to Table 3: Time and Events.

The Revised Conflict Tactics Scale [161] is a widely used measure of physical, psychological, and sexual aggression as well as injury and negotiation between partners. The scale consists of 39 conflict tactics, with respondents indicating the frequency with which they and their partner engage in each tactic, with each item presented as a "self" and "partner". Responses are given on a seven-point Likert scale where 0 = "This has never happened" and 6 = "More than 20 times in the past month", with 7 indicating occurrence in the past but not in the past year. The CTS2 contains four subscales; negotiation, psychological aggression, physical assault, and sexual coercion, and an injury score assessing impact of violence. CTS2 subscales are internally consistent, with alpha coefficients ranging from 0.79 to 0.95. Examining responses from relationship partners indicates high rates of agreement on responses. The CTS2 demonstrated construct validity, with scales demonstrating correlations with selected outcomes (for

instance, assault scale with injury). Research in a sample from a batterer-intervention program found moderate to good test-retest reliability (from 0.60 to 0.79) for all scales save sexual coercion [162]. Both the PTSD+ participant and the CSO participant will complete the CTS-2 according to Table 3: Time and Events.

The Inventory of Psychosocial Functioning (IPF) is a self-report instrument designed to assess functional impairment across spectrum of domains. The IPF [163] is an 80-item measure that that was developed for use among individuals with PTSD. It assesses current psychosocial functioning across seven domains: romantic relationships, family, work, friendships, parenting, education, and self-care. Responses are made on a 7-point Likert scale, from "never" to "always." Summation of scores across domains yields a total score for psychosocial functioning. The IPF has excellent psychometric properties [163, 164], with Cronbach's alpha for the total scale computed at 0.93 and good internal consistency for subscales (ranging from 0.80 to 0.90) [164]. IPF subscale scores possessed positive correlations with similar scales or subscales on other measures. Both the PTSD+ participant and the CSO participant will complete the IPF according to Table 3: Time and Events.

The Miller Social Intimacy Scale (MSIS) is a 17-item measure of the maximum level of intimacy currently experienced. The MSIS contains six items assessing the frequency of intimate contact and 11 items addressing intensity of contact, with all responses given on an 10-point Likert scale, with the total score assessing a single factor [165]. The MSIS can be used to measure social intimacy for people referring to an opposite sex or a same sex person and intimacy in close friends or romantic partners [166]. The MSIS is reliable, with Cronbach's alpha ranging from 0.84 to 0.95 [165, 166] and MSIS scores were positively related to scores on another measure of social intimacy [165]. Both the PTSD+participant and the CSO participant will complete the MSIS according to Table 3: Time and Events.

The Trauma and Attachment Beliefs Scale (TABS) was developed as a brief self-report measure of maladaptive beliefs about current life circumstances that may occur following trauma exposure [167]. The measure consists of 15 items, with responses made on a seven-point Likert scale with 1 = not at all true for you and 7 = completely true for you. This scale assesses maladaptive beliefs within three domains: (a) threat of harm, (b) self-worth and judgment, and (c) reliability and trustworthiness of others. After following procedures for reverse-scored items, scores are summed to produce scale scores for each domain. The TABS has an overall reliability of alpha of 0.82, with scale reliability ranging from 0.71 to 0.76. TABS scores exhibit a positive association with CAPS global severity scores, particularly for the Threat of Harm scale, and the scale had a negative association with scores on the PTGI. Both the PTSD+ participant and the CSO participant will complete the TABS according to Table 3: Time and Events. The CSO participant will complete a modified version.

The Multiscale Dissociation Inventory (MDI) is a 30-item self-report test of dissociative symptomatology in the last month, with responses made along a five-point Likert scale, with 1 = never and 5 = very often. It is fully standardized and normed, and measures six different type of dissociative response: disengagement, depersonalization, derealization, emotional constriction / numbing, memory disturbance, and identity dissociation. A total

dissociation score can also be calculated. Reliability for each subscale various from 0.74 for memory disturbance to 0.91 for derealization. The MDI has been found to have good psychometric qualities in both the normative and validation samples [168-170]. Both the PTSD+ participant and the CSO participant will complete the MDI according to Table 3: Time and Events.

The measure of state interpersonal closeness (IPC) is a 5-item non-verbal sponsor-developed self-report measure. Participants are asked to draw on a sheet of paper "how close you feel right now" to the self as observed, the Clinical Investigators, a selected significant other and "the world." Distance in mm between the self and each target will be considered an indirect measure of interpersonal closeness. The measure is expected to take between 2 and 4 minutes to complete. Both the PTSD+ participant and the CSO participant will complete the measures of interpersonal closeness according to Table 3: Time and Events.

The Couples Satisfaction Index (CSI) is a self-report 32-item scale designed to measure one's satisfaction in a relationship. The scale has a variety of items with different response scales and formats. The measure is expected to take approximately 5 minutes to complete. If the dyad is a romantic couple, both the PTSD+ participant and the CSO participant will complete the couples satisfaction index according to Table 3: Time and Events.

The therapists will assess General Wellbeing during each Preparatory Session, on each Integrative Session and during telephone calls for seven days. Results of this scale are intended to assist therapists in maintaining participant safety throughout the study. Both the PTSD+ participant and the CSO participant will be assessed according to Table 3: Time and Events.

